Research intervention	
This study is a Phase II clinical study of carradilimumab (AK 104) plus chemotherapy for PD-1 inhibitor-resistant nasopharyngeal cancer to evaluate the safety and efficacy of carradilimumab plus chemotherapy as second-line and above treatment for PD-1 inhibitor-resistant nasopharyngeal cancer. AK 104 has been approved for marketing and is not approved for nasopharyngeal cancer. The reasons for this study intervention in NPC are as follows: 1. Clinically, more and more NPC patients develop PD-1 inhibitor resistance. 2. A large amount of research evidence shows that the combination of PD-1 antibody and CTLA-4 antibody avoids the dark side of PD-1 antibody to some extent and effectively reduces the occurrence of PD-1 inhibitor resistance in

	
tumors. PD-1 and CTLA-4 complement each other and do not repeat in regulating immune responses, with mechanisms preventing T cell depletion and promoting T cell activation, respectively. When the PD-1 pathway and CTLA-4 modulation target the two pathways (Pardoll, 2012), they have more effective anti-tumor activity than single-agent therapy.

evaluation criterion:
 
Main end point:
 
Secondary end point:
 
safety evaluation:
	
Main end point
 
Safety: Incidence and severity of adverse events (AEs), clinically significant abnormal laboratory findings.
 
Based on the following data in RECIST v i. The ORR as assessed by the I.
 
Based on the following data in RECIST v i. I of the assessed PFS.
 
Secondary end point
 
According to the RECIST vi. The DoR, DCR, TTR, TTP, and OS as assessed by I.
 
PK characteristics: including serum concentrations of caadalinilimumab at different time points after caadabinibizumab administration.
 
Immunogenicity assessment: Number and percentage of subjects presenting with detectable antimicrobial antibodies (ADA).
 
To evaluate the correlation of PD-L1 expression with efficacy in immunohistochemical detection of tumor samples.
 
To evaluate the association of EB virus (EBV) DNA copy number in blood and antitumor activity of caadilimumab in subjects with advanced NPC.

	Health-related Quality of Life Assessment HRQoL-as measured using the European Organization for Research and Treatment of Cancer Quality of Life Questionnaire-Core 30 (EORTCQLQ-C30) and EORTCQLQ-H & N35.
statistical method:	

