## 1. foreword

### 1.1 research background

#### 1.1.1 General overview (must)

AK 104 is a humanized immunoglobulin G1 (IgG 1) bispecific antibody (BsAb) with crystallizable fragment (Fc) mutations to eliminate the Fc-receptor and complement-mediated cytotoxic effects. AK 104 is able to bind both programmed cell death receptor-1 (PD-1) and cytotoxic T lymphocyte-associated antigen-4 (CTLA-4) and block the interaction of PD-1 / programmed cell death ligand-1 (PD-L1), PD-1 / PD-L2, CTLA-4 / B7.1, and CTLA-4 / B7.2.

AK 104 is a tetravalent IgG-ScFv bispecific antibody. AK 104 contains a point mutation in its constant region that prevents the binding of the complement protein C1q and the Fc  $\gamma$  receptor involved in the cytotoxic effect. AK 104 is expressed in a Chinese hamster ovary cell line with a total molecular weight including oligosaccharides of about 200 kDa.

Therefore, this study aimed to evaluate the efficacy and safety of cadratinilizumab combination chemotherapy in patients with PD-1 inhibitor-resistant NPC and to determine its PK and immunogenicity characteristics to provide evidence for subsequent studies.

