## 1.2 Type of study (necessary)

This study is an interventional study, and all the drugs used in the study are already marketed. The target population is the second-line resistant NPC population, and there is no standard treatment plan in the diagnosis and treatment guidelines and principles. By exploring effective treatment options in such a patient population. There is clear preliminary study information on the efficacy and safety of any of the individual drugs used in this study protocol. This study is a single-arm exploratory study.

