### 1.4.3 discuss

Two phase Ib / II clinical studies. One was to evaluate the safety, tolerability, PK profile, immunogenicity, pharmacodynamics, and antitumor activity of AK 104 alone in advanced solid tumors and AK 104 in combination with oxaliplatin and capecitabine (mXELOX) in the first-line treatment of locally advanced or metastatic gastric adenocarcinoma or gastric esophageal adenocarcinoma. In terms of efficacy, as of April 30,2020, the ORR and 63.6% in 44 subjects with standard treatment failure. In the cohort of AK 104 combined with mXELOX for advanced gastric cancer or gastroesophageal adenocarcinoma, of 19 evaluable subjects, 2 CR, 11 PR, 5 SD, ORR reached 68.4% and 9 DCR reached 94.7%.

Tumor PD-1 inhibitor resistance is increasingly emerging in a large number of NPC patients. Regarding the biological mechanism of resistance to tumor PD-1 inhibitors associated with the upregulation of CTLA-4 expression. CTLA-4 binds more strongly to CD80 than CD28, thus resulting in CD80 endocytosis and downregulation of both antigen presentation capacity and T cell activity. Thus triggering PD-1 inhibitor resistance. Meanwhile, the researchers found that the combination of PD-1 / PD-L1 antibody and anti-CTLA-4 antibody (Ipilimumab and Opdivo-IO regimen) resulted in better tumor control in mice treated with anti-CTLA-4 alone or with PD-L1 antibody alone or control. The combination of PD-1 antibody and CTLA-4 antibody can be considered to avoid the dark side of PD-1 antibody to some extent, effectively reducing the occurrence of tumor resistance to PD-1 inhibitors. AK 104 is able to bind both programmed cell death receptor-1 (PD-1) and cytotoxic T lymphocyte-associated antigen-4 (CTLA-4) and block the interaction of PD-1 / programmed cell death ligand-1 (PD-L1), PD-1 / PD-L2, CTLA-4 / B7.1, and CTLA-4 / B7.2.

Therefore, this study aimed to evaluate the efficacy and safety of cadratinilizumab combination chemotherapy in patients with PD-1 inhibitor-resistant NPC and to determine its PK and immunogenicity characteristics to provide evidence for subsequent studies.

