### **4.2 Inclusion criteria (must)**

Subjects must meet all of the following inclusion criteria to be enrolled in the study:

Voluntary signed the written ICF.

- 1) Age was over 18 and 75 at the time of enrollment, acceptable for both men and women.
- 2) The Eastern Cooperative Oncology (ECOG) physical performance score was 0 or 1.
- 3) Expected survival is greater than 3 months.
- 4) Histologically or cytologically confirmed nasopharyngeal carcinoma.
- 5) The subject had previously failed treatment with PD-1 inhibitor and had no indication for radical local treatment.

6) According to the efficacy evaluation criteria of solid tumors RECIST v 1. And 1 with at least one measurable lesion.

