#### **4.3 Exclusion criteria (must)**

- Declaration that all baseline subjects meeting any of the exclusion criteria will be excluded from the study

- 1) Other than NPC, the subject had any other malignancy within 2 years prior to enrollment. Subjects who have been cured by local treatment of other tumors, such as basal or cutaneous squamous cell carcinoma, superficial bladder cancer, cervix or breast in situ carcinoma, are not excluded.
- 2) Attreatment the investigational drug within 4 weeks prior to the first study administration.
- 3) Having active autoimmune diseases requiring systemic therapy over the past two years (e. g. use of modifying medication, corticosteroids, immunosuppressive therapy), alternative therapy (e. g., thyroxine, insulin, or physiological corticosteroid replacement therapy for adrenal or pituitary insufficiency) is not considered a systemic therapy.
- 4) History of immunodeficiency; test positive for HIV antibodies; ongoing use of systemic corticosteroids or other immunosuppressants.
- 5) Active TB should be excluded in subjects with suspected active TB (TB).
- 6) Known history of allogeneic organ transplantation and allogeneic HSCT.
- 7) For subjects with untreated active hepatitis B (HBsAg positive with HBV-DNA over 1 000 copies / ml (200 IU / ml) or above the lower limit of testing, whichever higher), anti-hepatitis B treatment was required during study treatment; subjects with active hepatitis C (HCV antibody positive and HCV-RNA levels above the lower limit of testing).
- 8) Major surgery or severe trauma within 30 days prior to the first dose, or a major surgical planner within 30 days after the first dose (at the discretion of the investigator); a minor local procedure (excluding transperipheral venous

puncture central venous catheterization) within 3 days prior to the first dose.

- 9) The presence of CNS metastases.
- 10) Current uncontrolled concurrent conditions, including but not limited to symptomatic congestive heart failure (grade 2 or above under the New York Heart Association functional classification), unstable angina, acute myocardial ischemia, poorly controlled arrhythmia, decompensated cirrhosis, nephrotic syndrome, uncontrolled metabolic disorders, severe active peptic ulcer disease or gastritis, or psychiatric / social conditions that may limit study requirements or affect the subject's ability to provide written informed consent.

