17) Pregnant or lactating women.

18) Prior or current presence of any disease, treatment, laboratory abnormalities that may confuse the findings, affect the subject's full participation, or participation in the study may not be in the subject's best interest at the time.

19) Local or systemic disease due to nonmalignancy, or disease or symptoms secondary to tumor, and can lead to higher medical risk and / or uncertainty in survival evaluation, such as leukemic response (white cell count  $> 20 \times 10^9 / L$ ) or malmalignant manifestations (such as known weight loss of more than 10% in the 3 months prior to screening).

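### No eligibility criterion addresses prior AK 104 or other CTLA-4 antibody exposure, and the one interval rule that could cover prior anticancer drugs is unclear, so subjects who already failed the tested mechanism can enter the primary analyses

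*Protocol*

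**What the plan says.** **Rationale.** Protocol Section 1.3 presents CTLA-4 upregulation as a route to PD-1 inhibitor resistance. Section 1.4.3 repeats this: "Regarding the biological mechanism of resistance to tumor PD-1 inhibitors associated with the upregulation of CTLA-4 expression". Section 1.1.1 describes AK 104 as binding both PD-1 and CTLA-4.

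**Entry.** Inclusion 5 (Section 4.2) reads: "The subject had previously failed treatment with PD-1 inhibitor and had no indication for radical local treatment". It limits neither the agent, nor the number of earlier lines, nor the time since the last dose. Section 4 adds that disease must have progressed after a regimen containing a PD-1 inhibitor.

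**Exclusions (Section 4.3).**
- Item 2, after a garbled opening word: "the investigational drug within 4 weeks prior to the first study administration".
- Item 13 requires toxicity of earlier antitumour treatment to have recovered to grade 0 or 1, with stated exceptions. It sets no time.
- Item 18 excludes "Prior or current presence of any disease, treatment, laboratory abnormalities that may confuse the findings". It names no agent and no interval.

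**Availability of AK 104.** Section 1.2 says "all the drugs used in the study are already marketed". The synopsis says "AK 104 has been approved for marketing and is not approved for nasopharyngeal cancer".

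**Analysis sets.** The full analysis set (7.1.2) needs one dose and a measurable baseline lesion. The safety set (7.1.3) needs one dose. The synopsis assigns PFS to a randomized analysis set, which Section 7.1 does not define and which a single-arm trial cannot have.

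**The concern.** The scientific question concerns patients in whom PD-1 blockade alone has failed. AK 104 blocks PD-1 and is on the market, so a patient who progressed on it, or on a PD-1 antibody combined with a CTLA-4 antibody, can be said to have failed a PD-1 inhibitor. That patient cannot show whether adding CTLA-4 blockade helps, because it has already been tried. Counting such patients would tend to lower ORR and shorten PFS.

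The second gap works differently. No interval is fixed from marketed chemotherapy, radiotherapy or a PD-1 antibody to the first dose. A continuing effect of that treatment after baseline, or a late immune toxicity of the earlier antibody, would be attributed to the study regimen. Section 6.1 counts adverse events from entry whatever their cause, and safety is a primary endpoint in Section 2.2.1.

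The comparison is with historical data, so no concurrent arm would show either effect.

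**Working it through.** **Step 1. Which rules could apply to earlier anticancer drugs?** Section 4.3 has other interval rules on prior products: item 3 (systemic therapy for autoimmune disease, two years) and item 14 (live vaccine, 30 days). Neither concerns anticancer drugs. That leaves item 2, which has two readings.

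| Subject | Item 2 = any investigational drug | Item 2 = AK 104 itself |
|---|---|---|
| Failed marketed AK 104, last dose within 4 weeks | not barred | barred |
| Failed AK 104, last dose earlier than that | not barred | not barred |
| Failed another, marketed CTLA-4 antibody | not barred | not barred |
| Recent marketed chemotherapy, radiotherapy or PD-1 antibody | not barred | not barred |

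The gap remains under both readings. Once dosed, and with a measurable lesion, such a subject belongs to the full analysis set and the safety set. The same would hold for PFS whether its undefined set is taken as enrolled, treated or full analysis set.

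**Step 2. Scale.** The protocol gives no power calculation to reproduce; it plans 30 subjects with no formal hypothesis. One subject is 1/30 = 3.3 percentage points of ORR or of an adverse event incidence.

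The only reference rate is in Section 1.4.2: below 20% for chemotherapy in PD-1-resistant patients. Every other rate below, and every count k, is an assumption.

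*Expected dilution.* Suppose k pre-exposed subjects respond at 10% to 20% and the others at 40%. The loss in ORR is k/30 × (0.40 − 0.20) to k/30 × (0.40 − 0.10):
- k = 1: 0.7 to 1.0 points
- k = 3: 2.0 to 3.0 points
- k = 5: 3.3 to 5.0 points

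*Yardstick.* The exact 95% Clopper-Pearson lower limit first exceeds 20% at 12/30 (40.0%, interval 22.7% to 59.4%). This is not a decision rule of the protocol. The chance of reaching it, from the exact sum of two binomials, is:

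| k | Dilution: 40% in others, 10% in k. Expected ORR; P(≥12) | Carry-over: 20% in others, 40% in k. Expected ORR; P(≥12) |
|---|---|---|
| 0 | 40%; 0.57 | 20%; 0.009 |
| 3 | 37%; 0.43 | 22%; 0.019 |
| 6 | 34%; 0.30 | 24%; 0.035 |
| 9 | 31%; 0.18 | 26%; 0.062 |

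The two mechanisms push ORR in opposite directions.

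**Step 3. What a with/without analysis could show.** Take 9/30 responses, 30.0% (14.7% to 49.4%). If three non-responders were pre-exposed, the estimate without them is 9/27, 33.3% (16.5% to 54.0%). If six were, it is 9/24, 37.5% (18.8% to 59.4%).

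**The case against.** The case against has real weight on several points.

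- **Few may be affected.** AK 104 is not approved for nasopharyngeal carcinoma, so earlier use would be off-label or in another trial. This stands. Nothing in the protocol shows that any such subject would enrol.
- **Inclusion 5 has a narrower reading.** The examples of PD-1 inhibitors in Section 1.3 are pembrolizumab and nivolumab, and AK 104 is presented as the answer to resistance. An investigator may well not call AK 104 a PD-1 inhibitor. But the criterion does not say so, and a patient who failed a PD-1 antibody first and AK 104 later meets it on any reading.
- **Item 18 is a stated exclusion that names treatment.** It could catch some of these subjects. Without an agent or interval it works by case-by-case judgement, which in an open single-arm trial is itself a source of selection. Item 13 removes unresolved toxicity, not toxicity that has yet to appear.
- **Carry-over of tumour shrinkage is limited.** A reader might infer that shrinkage before baseline is credited to the study regimen. RECIST response is measured from baseline, so only shrinkage that continues afterwards could be. Section 4 requires progression after the PD-1-containing regimen, which makes continuing shrinkage from that regimen unlikely. The concern is left mainly with other recent treatment and with late immune toxicity.
- **The trial is exploratory.** With no formal hypothesis, no threshold is crossed. At 12/30 the interval is already far wider than the loss from one subject.

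**Conclusion.** The point holds as a gap in eligibility. Nothing in Sections 4.2 and 4.3 addresses prior AK 104 or other CTLA-4 antibody exposure. Item 2 is the only interval rule that could cover prior anticancer drugs, and its meaning is unclear. Inclusion 5 as written does not match the rationale in Sections 1.3 and 1.4.3.

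The size is up to 3.3 points of ORR or adverse event incidence per affected subject. The number affected is not given, and the net direction is unknown. The larger figures above depend wholly on the assumed 40%, 20% and 10% rates and on the assumed k.

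A reader might go further and infer that such subjects will be counted, that item 2 is the only interval rule on any prior drug, or that the results are biased by a known amount. The documents support none of these. Such subjects can be counted, items 3 and 14 are also interval rules, and no bias can be quantified from the protocol. This is a worthwhile, inexpensive correction, not a flaw that invalidates the trial.

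**What to change.** 1. Bring inclusion 5 into line with the rationale by adding one item to Section 4.3: prior treatment with AK 104 or any other CTLA-4-blocking antibody excludes the subject. The cost is one line and perhaps a few lost candidates.
2. Reword item 2 so that it says which drugs it covers, and state whether its existing interval extends to marketed anticancer treatment. The length of any such interval is a clinical decision for the sponsor, and none is proposed here.
3. If subjects with such exposure or recent treatment stay eligible, pre-specify ORR, PFS and adverse event incidence with and without them. Section 9.4.1.2 already has prior oncology treatments in the case report form. The extra work is small provided that agent and last-dose date are captured. With 30 subjects this analysis would be descriptive only.

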	
tolerance are good and initial efficacy signals are observed, the extended enrollment phase will enter. Efficacy analysis will be performed for approximately 15 subjects. If 6 of the 15 subjects are not tolerated, subject enrollment may be stopped after the investigator discussion. After poor safety, the investigator decided to revise or stop the study. For 4-6 cycles, the use of caldulizumab until the investigator determines that there is no clinical benefit (based on the comprehensive judgment of RECISTv1.1 imaging assessment and clinical symptoms), toxicity intolerance, completion of 24 months of treatment, or satisfaction of other criteria for treatment termination in the regimen, whichever occurs first.
 
 
• Subject treatment protocol:
 
• Caradilizumab (200 mg, administered on Day 1, Q3W until no longer clinical benefit) + platinum-based chemotherapy, Q3W, 4-6 cycles), treatment cycle every 3 weeks (21 days).
 

Total number of enrolled patients	30 Cases
Number of research groups Number of control groups	The number of the study group was 30 cases
diagnose	nasopharyngeal darcinoma
Selection criteria	
Selection criteria:
 
Subjects must meet all of the following inclusion criteria to be enrolled in the study:

[figure not shown]
	
Voluntary signed the written ICF.
 
 
1) Age was over 18 and 75 at the time of enrollment, acceptable for both men and women.
 
2) The Eastern Cooperative Oncology (ECOG) physical performance score was 0 or 1.
 
3) Expected survival is greater than 3 months.
 
4) Histologically or cytologically confirmed nasopharyngeal carcinoma.
 
5) The subject had previously failed treatment with PD-1 inhibitor and had no indication for radical local treatment.
 
6) According to the efficacy evaluation criteria of solid tumors RECIST v 1.1 with at least one measurable lesion.
 

Exclusion criteria	

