- 11) There was a past history of myocarditis, cardiomyopathy, and malignant arrhythmia. Unstable angina, congestive heart failure, or vascular disease (such as aortic aneurysm or peripheral venous thrombosis requiring surgical repair) within 2 months before the first dose, Or other cardiac lesions that may affect the safety evaluation of the study drug (e. g. poorly controlled arrhythmias, Myocardial infarction or ischemia); presence of esophageal-gastric varices within 6 months before the first dose, Severe ulcer, The wound has not healed, gastric-intestinal perforation, abdominal pain, Gastrointestinal obstruction, History of intra-abdominal abscess or acute gastrointestinal bleeding; any arterial thromboembolic event within 6 months prior to the first dose, NC I CTCAE 5.0 grade 3 and above, Transient cerebral ischemic attack, cerebrovascular accident, Hypertensive crisis or hypertensive encephalopathy; acute exacerbation of chronic obstructive pulmonary disease within 1 month before the first dose; current presence of hypertension with SBP> 160mmHg or DBP <100mmHg after oral antihypertensive medication.
- 12) History of severe bleeding tendency or coagulationopathy; blood symptoms of significant clinical significance within 1 month before the first dose, including but not limited to gastrointestinal bleeding, hemoptysis, screening imaging showing tumor wrapping around important blood vessels or significant necrosis and emptiness, and the investigator believes that participation in the study may

cause bleeding risk;

13) No response of prior anti-tumor therapy, defined as not returning to Grade 0 of NC 1 CTCAE 5.0 or 1, or the level specified in the inclusion / exclusion criteria, except for sequelae of alopecia, neurotoxicity associated with prior lead therapy. Subjects with irreversible toxicity not expected to worsen after study drug administration (e. g. hearing loss) may be included in the study after consultation with the medical monitor. Long-term toxicity from radiotherapy, subjects not recoverable as judged by the investigator may be included in the study after consultation with the medical monitor.

14) Live vaccination was administered within 30 days before the first dose, or was planned to be administered during the study period.

15) Known allergy to any component of any study drug; known history of severe hypersensitivity to other monoclonal antibodies.

16) Known history of mental illness, substance abuse, alcohol abuse, or drug use.

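### Exclusion 11, as printed, points its two blood-pressure limits in opposite directions: it excludes a treated hypertensive patient at 150/95 and does not exclude one at 150/110

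*Protocol*

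**What the plan says.** Section 4.3 opens with the rule that one criterion is enough: "Declaration that all baseline subjects meeting any of the exclusion criteria will be excluded from the study". Item 11 is a long list of cardiovascular and related conditions. Among the events it lists are "Transient cerebral ischemic attack, cerebrovascular accident, Hypertensive crisis or hypertensive encephalopathy". It closes with the blood-pressure clause: "current presence of hypertension with SBP> 160mmHg or DBP <100mmHg after oral antihypertensive medication".

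Three other items in Section 4.3 could bear on a patient with raised blood pressure, all in general terms:

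- Item 10 covers "Current uncontrolled concurrent conditions, including but not limited to" a list of named conditions. Hypertension is not among them.
- Item 18 covers conditions because of which "participation in the study may not be in the subject's best interest at the time".
- Item 19 covers disease that "can lead to higher medical risk and / or uncertainty in survival evaluation".

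None of these gives a blood-pressure figure. The row for exclusion criteria in the scenario summary shows no text in the version at hand. It therefore cannot settle the point, and the gap is not counted as a fault.

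**The concern.** A clause meant to keep out patients whose hypertension is not controlled on treatment would be expected to exclude upward on both pressures. Here the systolic limit excludes upward and the diastolic limit excludes downward. The clause can be met, so it is not a logical contradiction, but its diastolic half works against its own subject, which is hypertension persisting on treatment. It also sits badly with the rest of item 11, which is concerned with the consequences of high pressure.

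This is a rule applied to each patient at screening. Anyone following it literally would turn away treated patients with the lower diastolic readings and let through those with the higher ones. Anyone who noticed the oddity would have to guess the intended direction, and also whether a diastolic of exactly 100 counts. Different staff could guess differently.

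The criterion is not an idle one for this drug. The AK104 monotherapy safety table in Section 1.1.2 lists 2 treatment-related cases of hypertension among 228 subjects, both of grade 3 or 4. That is a small number and is mentioned only to show relevance.

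**Working it through.** The protocol gives no calculated figure to reproduce on this point. The check is to apply the printed rule to readings.

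**Inputs, all from Section 4.3**

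- Systolic limit (item 11): excluded if SBP > 160 mmHg.
- Diastolic limit (item 11): "DBP <100mmHg after oral antihypertensive medication", that is, excluded if DBP < 100 mmHg.
- Connector: or.
- Effect: meeting any criterion excludes the patient (opening statement).

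**Rule as printed:** excluded if SBP > 160 or DBP < 100.

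The two limits divide readings into six zones: SBP above 160, or 160 and below, crossed with DBP below 100, exactly 100, or above 100. Each rule below gives the same decision throughout a zone, so one reading per zone is enough. Two comparison rules, in which both limits run upward, are included only to show where the printed direction matters. They are not proposals.

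- Comparison A: SBP > 160 or DBP > 100.
- Comparison B: SBP > 160 or DBP ≥ 100.

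| Reading | SBP > 160? | DBP < 100? | Printed rule | Comparison A | Comparison B |
|---|---|---|---|---|---|
| 165/95 | yes | yes | excluded | excluded | excluded |
| 165/100 | yes | no | excluded | excluded | excluded |
| 165/110 | yes | no | excluded | excluded | excluded |
| 150/95 | no | yes | excluded | not excluded | not excluded |
| 150/100 | no | no | not excluded | not excluded | excluded |
| 150/110 | no | no | not excluded | excluded | excluded |

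**Results**

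- The printed rule excludes 4 of the 6 zones (the three at 165, and 150/95). It spares 2 (150/100 and 150/110).
- It differs from comparison A in 2 of 6 zones (150/95 and 150/110).
- It differs from comparison B in 3 of 6 zones (150/95, 150/100 and 150/110).
- Every differing zone has SBP of 160 or less. Above 160 the systolic limit alone decides, and the diastolic sign has no effect.
- At the boundary, 160/100 and 160/120 are both not excluded by the printed rule.
- A treated hypertensive patient at 130/80 falls in the same zone as 150/95 and is excluded.

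The zones are of unequal and unknown size, so these counts describe where decisions change. They do not say how many patients are affected.

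**Can another criterion repair the clause?** Items 10, 18 and 19 could let an investigator exclude the patient at 150/110 by judgement. They supply no limit, and because they only exclude, they cannot re-admit the patient at 150/95.

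**The case against.** The strongest objection is that the fault lies in the English text and not in the plan. The document is plainly a rough translation, and comparison wording elsewhere is unreliable. The age criterion in Section 4.2 has lost the wording of its upper limit, and the description of the safety table in Section 1.1.2 has lost the signs that its rows imply. The study names one hospital in China, so screening may well use a source-language text that is correct. This makes a slip plausible, and it is accepted here as the likely explanation. It remains unproven, though. The other examples are mostly lost signs, whereas here a definite sign is printed and points the opposite way to its neighbour.

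A second objection is that the error gives itself away. The literal rule turns away any treated hypertensive patient with a diastolic below 100, so staff would probably notice at the first such screening. Items 10 and 18 would also let them exclude a patient with a high diastolic pressure. Both points lower the practical risk. But noticing that something is wrong does not tell the reader what was intended, and discretion to exclude does not re-admit anyone.

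A third point is narrower. The 130/80 example assumes that a patient whose pressure is normal on treatment still counts as currently having hypertension. If the phrase refers to the current reading, that example falls away. The finding does not depend on it: 150/95 and 150/110 carry it.

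**Conclusion.** The concern holds for the text as printed. The two limits in item 11 run in opposite directions. At any systolic pressure of 160 or less, the clause excludes the lower diastolic values and spares the higher ones. Compared with a reading in which both limits run upward, decisions change in 2 or 3 of the six zones, depending on how a diastolic of exactly 100 is treated.

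What the clause says as printed is certain. Whether the source-language protocol carries the same error cannot be determined from this document. The protocol gives no blood-pressure data for candidates, so no number of wrongly excluded or wrongly admitted patients is offered. No effect on the sample size, endpoints or analyses is claimed. The point should be fixed because it is a safety-related eligibility rule applied to every patient and nothing else in the protocol states the intended limit.

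**What to change.** Check the closing clause of Section 4.3, item 11, against the source-language protocol. Reconcile the direction of the systolic and diastolic limits, and make plain whether a reading exactly at each limit is excluded. Carry the same wording into any eligibility form or screening checklist derived from the protocol. The thresholds are for the investigators to set, and none is proposed here.

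The cost is one comparison with the source text and, if the slip is confirmed, a one-line correction in the protocol and in any derived form.

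### Exclusion 13 screens earlier PD-1 inhibitor toxicity by current grade only, so a resolved severe non-cardiac irAE is not expressly excluded and needs no medical-monitor discussion at entry

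*Protocol*

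**What the plan says.** Protocol 4.2, item 5, makes earlier exposure universal: "The subject had previously failed treatment with PD-1 inhibitor".

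Protocol 4.3, item 13, deals with toxicity left over from earlier anti-tumour treatment. Its opening words are garbled in translation, but the test is clear. A subject is excluded for toxicity "defined as not returning to Grade 0 of NC 1 CTCAE 5.0 or 1", or to another level set in the criteria, with named exceptions. The item asks for medical-monitor consultation in two situations only: irreversible toxicity not expected to worsen, and long-term radiotherapy toxicity judged unrecoverable.

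Other items in 4.3 bear on the question:
- Item 3: "Having active autoimmune diseases requiring systemic therapy over the past two years".
- Item 4: "ongoing use of systemic corticosteroids or other immunosuppressants".
- Item 11: "There was a past history of myocarditis, cardiomyopathy, and malignant arrhythmia", and a six-month gastrointestinal clause that includes "History of intra-abdominal abscess or acute gastrointestinal bleeding".
- Item 15: a history of severe hypersensitivity to other monoclonal antibodies.
- Item 18: excludes, among other grounds, where "participation in the study may not be in the subject's best interest at the time".
- Item 19: covers conditions that "can lead to higher medical risk and / or uncertainty in survival evaluation".

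Table 2 in 8.4 sets out what to do with AK 104 when an irAE occurs on study. Sections 1.4.1 and 8.4 both allow AK 104 to be resumed after a grade 3 or 4 event if the toxicity resolved quickly, once the medical monitor has been consulted.

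**The concern.** AK 104 blocks PD-1 and CTLA-4, so it acts again on the pathway that every subject has already had blocked. The worst grade of an earlier irAE is therefore relevant to whether the drug should be started. Item 13 does not ask for it. A subject whose grade 4 pneumonia on a PD-1 inhibitor has settled to grade 0-1, and who is off steroids, passes item 13 and meets no exclusion that names the event.

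The stake is subject safety, which is also a primary endpoint (2.2.1). The lead-in has about six subjects, so one recurrence there would weigh heavily in the decision to expand. No sample size, error rate or efficacy estimate depends on the point.

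**Working it through.** No formula applies and the plan gives no figure to reproduce. The check sets Table 2 against 4.3.

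**Step 1. Table 2 rows.** There are 10: pneumonia, diarrhoea/enteritis, AST/ALT, type 1 diabetes or hyperglycaemia, hypophysitis, hyperthyroidism, hypothyroidism, nephritis, carditis, and all other irAEs.

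**Step 2. Rows with a level at which the only listed action is permanent withdrawal.** There are 6: pneumonia, enteritis, AST/ALT, nephritis, carditis and other irAEs. The four endocrine rows either continue treatment, suspend it, or leave the choice between suspension and withdrawal.

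**Step 3. What 4.3 says about a resolved event at those levels on the earlier PD-1 inhibitor.**

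| Table 2 row | Permanent-withdrawal level | Express exclusion once resolved? |
|---|---|---|
| Carditis | Grade 3-4 | Yes: item 11, past myocarditis |
| Pneumonia | Grade 3-4, or recurrent grade 2 | No |
| Enteritis | Grade 4 | Not as such; item 11 catches some recent complications |
| AST/ALT | Grade 4 | No |
| Nephritis | Grade 3-4 | No |
| Other irAE | Grade 4, or recurrent grade 3 | No |

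6 − 1 = 5 rows have no item that names the resolved event.

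**Step 4. Items that could still catch it.**
- Item 3 has a two-year look-back and mentions corticosteroids. It concerns active autoimmune disease, whereas 1.4.1 and 8.4 define an irAE as an adverse event associated with drug exposure. Whether a resolved irAE qualifies is arguable.
- The steroid and immunosuppressant clause of item 4 stops applying once treatment ends.
- The six-month clause of item 11 reaches perforation, bleeding, obstruction, severe ulcer and abdominal pain, so much recent severe enteritis would be caught. It does not reach older enteritis or the other four rows.
- Items 18 and 19 can reach any of these histories, but only by judgement. They name no irAE, set no grade and call for no medical-monitor contact.

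**Step 5. Comparison with the protocol's own practice.**
- Items 11 and 15 screen history for two toxicities that also stop AK 104 on study: carditis in Table 2, and severe hypersensitivity in 8.2. The protocol therefore already accepts screening history for stopping toxicities.
- Return to grade 0-1 is also the recovery level that the notes to Table 2 use for restarting AK 104 after a suspension. Item 13 adopts that recovery level but has no counterpart to the permanent-withdrawal levels.
- Item 13 sends irreversible toxicity such as hearing loss to the medical monitor, but not a resolved life-threatening irAE.
- On study, resumption after a grade 3 or 4 event needs the medical monitor. At entry, a comparable event on the earlier drug does not.

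**Step 6. Frequency.** The documents give no rate of such histories after PD-1 inhibitor treatment. The AK 104 monotherapy table in 1.1.2 concerns a different drug, pools grades 3 and 4, and has no rows for pneumonia or enteritis. It cannot supply the number, and none is calculated here.

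**The case against.** The strongest reply is that nothing in the protocol is contradicted. Recovery to grade 0-1 is a legitimate requirement, and Table 2 governs toxicity on AK 104, not past toxicity on another drug. Its title presents its content as recommendations, and the text after it sends conflicts with other guidelines or local practice to a meeting organised by the investigator. Item 18 looks back at prior disease and treatment, and subjects who meet any exclusion are to be excluded. The comparison with on-study resumption is also imperfect, because restarting the same drug soon after an event differs from starting another drug after an older, resolved one. Section 4 also requires progression, which may leave fewer subjects who stopped a PD-1 inhibitor for toxicity.

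Most of this stands, and it limits the point. A reader might infer that the protocol contradicts itself, or that such subjects enter with no safeguard. The documents support neither: Table 2 does not address earlier drugs, and item 18 can exclude. A reader might also want a probability that at least one of the 30 subjects has such a history. That would need assumed event counts with no source in the documents. Nor is the resumption wording in 1.4.1 and 8.4 in conflict with Table 2, since the table allows restart after several grade 3 events and after controlled grade 3-4 endocrine events.

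What the reply does not remove is that item 13, followed as written, clears such a subject unless someone chooses to invoke a general clause, and that nobody outside the site has to be consulted.

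**Conclusion.** The point holds as a limited safety gap in eligibility. For five of the ten Table 2 rows, a resolved irAE on the earlier PD-1 inhibitor at a level where the table recommends permanent withdrawal of AK 104 is not expressly excluded. It is reachable by judgement, mainly through item 18, and in part through items 3 and 11. No medical-monitor discussion is required at entry.

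The number affected cannot be stated from the documents and is probably small; the reason to act is the possible severity for each such subject. The conclusion assumes that item 13's garbled opening refers to unresolved toxicity, as the rest of the item indicates, and that a resolved irAE is not automatically an active autoimmune disease under item 3. If item 3 were read to include it, cases needing systemic treatment within two years would be covered and the gap would narrow to older ones.

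**What to change.** Add one item to 4.3: a subject whose irAE on an earlier checkpoint inhibitor met a level at which Table 2 recommends permanent withdrawal of AK 104 may start AK 104 only after documented agreement of the medical monitor, or is excluded. The first option is the minimum and uses a step the protocol already has. Screening would need to record the worst grade and any recurrence of earlier irAEs, not only their present grade.

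The cost is one line of text, that extra history at screening, and the possible loss of a rare candidate; under the medical-monitor option there may be no loss. No change to 1.4.1, 8.4 or Table 2 is needed.
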